## **STUDY PROTOCOL**

### **»Impact of Consumption of Beta-glucans on the Intestinal Microbiota and Glucose and Lipid Metabolism«**

#### **Introduction**

Metabolic syndrome (MS) is a complex lifestyle disease manifesting metabolic disorders such as abdominal obesity, dyslipidemia, hyperglycemia and hypertension. There are many studies reporting how gut microbiota correlates with metabolic disorders or contributes to the development of obesity through increased energy harvest. An increasing interest in finding the diet that could regulate the composition of gut microbiota and consequently improve the individual conditions related to some of the metabolic disorders, exists. The aim of our study will be to investigate, whether consumption of barley beta glucans can positively modulate the composition of gut microbiota and metabolic parameters related to MS. Barley beta glucans are polysaccharides found in kernel endosperm and improve both lipid and glucose metabolism. The effects of barley beta glucans on gut microbiota composition are still poorly investigated in human clinical trials.

We will perform a double-blind, placebo controlled, randomized clinical trial with volunteers diagnosed with MS. The exact study protocol and procedure will be explained to the participants, who will meet inclusion criteria. After assignment of participation agreement, participant will be randomized and allocated to test or placebo group. Before and after the dietary intervention, anthropometric measurements, blood analysis, including oral glucose tolerance testing (OGTT), and fecal sampling will be performed. Participants will daily complete food frequency questionnaire and detailed 72-hour dietary recall. During intervention participants will daily consume test bread with added 6g beta glucans or bread without added beta-glucans.

The study was approved by the Republic of Slovenia National Medical Ethics Committee (112/08/13).

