### 1.1. Objective

The purpose of this study was to investigate if daily consumption of barley beta-glucans effect lipid and glucose metabolism and alter intestinal microbiota composition in participants with metabolic syndrome or with high risk for metabolic syndrome development. We conducted 4-week long, placebo controlled dietary study, where participants consumed bread with (test group) or without (control group) enriched beta-glucans bread.

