### 1.2. Hypothesis

1. 4- week consumption of beta-glucans alters the composition of intestinal microbiota and changes the ratio of different bacteria groups and consequently effects production of short chain fatty acids in a population with metabolic syndrome or with high risk for metabolic syndrome development.
2. 4- week consumption of beta-glucans has an influence on glucose metabolism and consequently improves insulin resistance within people with metabolic syndrome or with high risk for metabolic syndrome development.
3. 4 - week consumption of beta-glucans improves specific plasma lipid content in a population with metabolic syndrome or with high risk for metabolic syndrome development.

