## 2. STUDY METHODS

### 2.1. Trial design and participants enrolment

[figure not shown]
Study was performed as double blind, randomised, placebo controlled clinical trial and was performed regarding to CONSORT 2010 recommendations for randomised clinical trials [1]. The study was approved by the Republic of Slovenia National Medical Ethics Committee (112/08/13). Participant enrolment was performed within a national programme for metabolic disorder prevention in community health centres in Slovenia in association with family medicine doctors. Participants that met including criteria and had metabolic syndrome or high risk for metabolic development were suggested to participate in clinical trial.

Table 1: **INCLUSION CRITERIA**

Parameter	Inclusion criteria*
Age	30 – 70 years
Total cholesterol levels	$\geq 5.0 \text{ mmol/L}$
Waist circumference	Women $> 80 \text{ cm}$ Men $> 94 \text{ cm}$
And presence of at least one of the remaining determinants for MS	
HDL-cholesterol	Women $< 1.29 \text{ mmol/L}$ Men $< 1.03 \text{ mmol/L}$
Raised blood pressure	Systolic blood pressure $\geq 130 \text{ mm Hg}$ Diastolic blood pressure $\geq 85 \text{ mm Hg}$
Raised fasting plasma glucose	$\geq 5.6 \text{ mmol/L}$

\*Participants diagnosed with metabolic syndrome and meeting the age criteria were directly included in the study. Exclusion criteria were diabetes type II, thyroid disorders, kidney disorders and antibiotic treatment.

Participants who met the inclusion criteria started the intervention after agreement with study conditions and procedures. Participants that agreed to participate were randomised and enrolled in trial as the control or test group (Figure 1).

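### The protocol names volunteers diagnosed with metabolic syndrome; the SAP also covers people at high risk and plans no estimate for participants with the syndrome

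*Protocol*

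**What the plan says.** The protocol's Introduction sets the design as a "double-blind, placebo controlled, randomized clinical trial with volunteers diagnosed with MS". It refers to inclusion criteria but lists no thresholds. Its section A form has fields for age, body size, certain conditions and treatment, total cholesterol and BMI, and none for a diagnosis of MS.

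The SAP uses a wider population throughout. The objective (section 1.1) is to study effects "in participants with metabolic syndrome or with high risk for metabolic syndrome development". All three hypotheses in section 1.2 use that population; the third, for example, is that beta-glucan consumption "improves specific plasma lipid content in a population with metabolic syndrome or with high risk for metabolic syndrome development". The enrolment text in section 2.1 reads "Participants that met including criteria and had metabolic syndrome or high risk for metabolic development were suggested to participate in clinical trial".

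Table 1 of section 2.1 then sets thresholds for age, total cholesterol and waist, with the further condition "And presence of at least one of the remaining determinants for MS". Its footnote gives a second way in: "Participants diagnosed with metabolic syndrome and meeting the age criteria were directly included in the study".

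Section 3 of the SAP specifies paired tests for the metabolic outcomes and a DESeq2 model with time, group and subject for the sequencing data. MS status and entry route appear in neither. Section 1 says that the SAP was prepared when the trial was completed.

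**The concern.** The two documents name different populations, and neither explains or dates the change. A reader who takes the population from the protocol will read the results as effects in people with diagnosed MS. The planned analysis gives effects in a mixture whose make-up the readable text does not report.

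What is at stake is interpretation. If the effect of beta-glucans depends on MS status, the pooled figure describes neither group, and nothing in section 3 would show it. Because the SAP was written after completion, the wider population also cannot be shown from these documents to have been planned in advance.

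**Working it through.** The documents state no sample size, power, effect size, standard deviation or count by MS status, so there is no figure of the plan to reproduce. The check is a comparison of texts.

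**Step 1: the two entry rules (SAP section 2.1, Table 1 and footnote).**

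| Criterion | Diagnosed MS (footnote) | Table 1 |
|---|---|---|
| Age 30–70 years | required | required |
| Recorded MS diagnosis | required | not required |
| Total cholesterol ≥ 5.0 mmol/L | not required | required |
| Waist > 80 cm (women), > 94 cm (men) | not required separately | required |
| At least one of low HDL, raised blood pressure, raised fasting glucose | not required separately | required |

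A person with a diagnosis needs only the age criterion. The remaining thresholds therefore decide entry only for people without one, and those people are not covered by the protocol's design sentence.

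**Step 2: the analysis (SAP section 3).** There is no stratum, covariate, subgroup or sensitivity analysis for MS status or entry route, in the paired tests or in the DESeq2 model. Everyone is pooled, and no estimate in participants with MS is planned.

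**Step 3: can the direction of the difference be found?** Let q be the share of participants without MS, and r their effect divided by the effect in participants with MS. The pooled effect as a fraction of the MS effect is

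f = (1 − q) + q·r, so f − 1 = q·(r − 1).

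The sign depends only on whether r is below or above 1, and the size depends on both q and r. The documents give neither. The entry rules point both ways:

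- Glucose and insulin: Table 1 can be met without raised fasting glucose, so people entering that way may have less room to improve (r below 1).
- Total cholesterol: Table 1 requires at least 5.0 mmol/L and the direct route does not, so people entering by Table 1 may have more room for a fall (r above 1).

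Any percentage for dilution or lost power would come from the chosen q and r, so none is given.

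**Step 4: does pooling distort the comparison of arms?** Section 2.1 has participants randomised after they met the criteria and agreed to take part. A mixed eligible population does not in itself confound the arms. No stratification by MS status is described, so chance imbalance is possible, but nothing shows that it occurred.

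**Step 5: can MS status be recovered?** The section A form has no diagnosis field. Sections B1 and B2 of the protocol do collect baseline waist, HDL-cholesterol, triglycerides, blood pressure and fasting glucose, so status could be derived where no diagnosis was recorded, once the sponsor states the definition used. Neither document gives one.

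**The case against.** The strongest reply is that the protocol's question is broader than its design sentence. Its aim is to find out whether "consumption of barley beta glucans can positively modulate the composition of gut microbiota and metabolic parameters related to MS"; that sentence names no diagnosed population, and people with diagnosed MS remain in the sample. The protocol also says that the study will be "explained to the participants, who will meet inclusion criteria", which allows for criteria set out elsewhere. This stands against the inference that the trial fails to answer the protocol's question. It does not remove the mismatch with the design sentence or supply an estimate for MS.

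Three further points stand:

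- Entry by Table 1 does not mean that a person was only at high risk. The requirement of one further determinant is a minimum, so some may have had several determinants and undiagnosed MS. Entry route is not a clean split between MS and no MS.
- The SAP already uses the wider population in its objective and hypotheses, so conclusions in those words would agree with the SAP.
- The flow diagram is not reproduced in the text available, so it cannot be said that counts by entry route are missing from the plan.

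A reader might also infer that the SAP's authors widened the population after seeing results. The documents do not support that. The SAP describes who was enrolled, and neither document says when the wider rule was adopted.

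**Conclusion.** The concern holds as a discrepancy between protocol and SAP with a consequence for interpretation: the pooled result is not an estimate for the population named in the protocol's design sentence, and no such estimate is planned.

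Its numerical size is undetermined. A reader might infer that the effect is diluted and power lost; that would need r below 1, which the documents do not establish and which the cholesterol criterion could reverse. A reader might also infer a biased comparison of arms; with randomisation after eligibility, none is shown.

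The conclusion assumes that the footnote means what it says, namely that diagnosed MS plus age was enough, and that section 3 is the complete analysis plan. It is a modest point, worth acting on because the remedy is cheap.

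**What to change.** 1. Reconcile the population in the protocol's Introduction with SAP sections 1.1, 1.2 and 2.1, correct whichever does not describe who was enrolled, and state when and why the population was widened.
2. Report numbers by MS status and arm. Use the recorded diagnosis where there is one; otherwise derive status from the baseline determinants in protocol sections B1 and B2, and state the definition applied.
3. Add to SAP section 3 a between-arm comparison of changes in participants with MS, or a group-by-MS-status interaction, with its interval, next to the pooled between-arm estimate. Label it post hoc. For the metabolic outcomes section 3 now has only paired tests, so the pooled between-arm estimate has to be added too.
4. Limit conclusions to people with MS or at high risk unless that analysis supports a statement about MS.

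The cost is some rewording, one table of counts and a small amount of extra analysis. The MS estimate will have a wide interval: the only counts in the readable text are 14 test and 9 control participants, in the sequencing subset, and a part of those would be very imprecise. Recovering MS status may mean going back to clinic enrolment records, and derived status will be less certain than a recorded diagnosis.

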## Study protocol

### A) Participants information and inclusion criteria

Name	
Surname	
Age	
Body height & body weight (cm, kg)	
Diabetes type 2	
Kidney dysfunction	
Thyroid dysfunction	
Treatment for hypercholesterolemia (not hypertension)	
Total cholesterol (mmol /l)	
Body Mass Index (BMI)	

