### B) Before and after intervention: Blood test Analysis and Anthropometric measurements

#### 1. Lipid profile, Anthropometric measurements

Parameter	Before dietary intervention	After dietary intervention
Total cholesterol (mmol/l)		
LDL-cholesterol (mmol/l)		
HDL-cholesterol (mmol/l)		
Triglycerides (mmol/l)		
Blood pressure (mmHg)		/
Body weight (kg)		
Body waist (cm)		

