**Figure 1: Participants flow diagram.**

## 2.2. Dietary intervention

Participants consumed bread with beta-glucans content of approximately 3,4 g beta-glucans per 100 g of bread in 4-week long intervention. Before study participants had two-week washout period without consuming any pre- and pro-biotics. Participants retained their usual eating habits during the

intervention. A 72-hour dietary recall was performed in order to control participants' diet and eating habits. Participants were told to consume 200 g of bread daily, not knowing whether the bread was experimental or control. Participants included in the test group consumed 200 g of BGB, containing more than 6 g of barley beta glucans, daily. Participants in the control group consumed 200 g of CWB without added beta glucans. 72-hour dietary recall was performed before intervention and at the end of the trial to evaluate daily nutrient and energetic input of each participant.

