### 2.3. Primary outcome measures

Participants gave blood and stool samples a day before intervention with barley beta-glucans. Blood sampling was performed for insulin resistance determination and for lipid profile determination (Total cholesterol, HDL-cholesterol, LDL-cholesterol, triglycerides). They also had option to give a blood sample for genetic investigation of genes associated with lipid metabolism (apoE).

Analysis were performed in accordance with health community centres in Ajdovščina and Ljubljana, Slovenia. Venous blood samples were obtained by professional medicine personnel for analysis of fasting glucose, lipids and insulin.

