## 2.4. Secondary outcome measures

After 4 weeks of dietary intervention protocol of primary outcome measures was repeated.

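### Total cholesterol is recorded at inclusion and again before the intervention, but the plan has only paired before/after tests for it: add a between-arm ANCOVA, with the inclusion value as a second covariate if it is a separate draw

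*Protocol*

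**What the plan says.** - **Inclusion form.** Protocol, part A, has one field, "Total cholesterol (mmol /l". It gives no draw date, laboratory or source.
- **Before/after form.** Protocol, part B, section 1, has "Total cholesterol (mmol/l" with a before and an after column.
- **Timing.** SAP Section 2.3: "Participants gave blood and stool samples a day before intervention with barley beta-glucans". SAP Section 2.4: "After 4 weeks of dietary intervention protocol of primary outcome measures was repeated".
- **Entry rule.** SAP Table 1 lists "Total cholesterol levels" at 5.0 mmol/L or more. Its footnote opens a second route: "Participants diagnosed with metabolic syndrome and meeting the age criteria were directly included in the study".
- **Washout.** SAP Section 2.2: "Before study participants had two-week washout period without consuming any pre- and pro-biotics".
- **Analysis.** SAP Section 3 (Statistics) assigns anthropometric and metabolic characteristics to a paired t-test or Wilcoxon signed-rank test. The only model with a group term is the DESeq2 interaction model, which is for sequence abundance. Total cholesterol also defines responders in the test group (a 10% fall). The SAP does not define the baseline value and does not mention the inclusion value.

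**The concern.** A single cholesterol reading carries within-person variation, and in a four-week comparison that variation is part of the error. A second reading taken before randomisation says more about each person's usual level. It cannot be affected by allocation, so adjusting a between-arm comparison for it adds precision without bias.

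The plan is not set up to use it. A paired test within each arm takes one before value, has no place for a covariate, and does not compare beta-glucan bread with control bread. Two things are therefore at stake for cholesterol: the randomised comparison itself, which is the larger matter, and some precision within that comparison once it exists.

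**Working it through.** The documents state no sample size, SD, correlation or power for cholesterol, so there is no figure of the plan's to reproduce. All correlations, means and SDs below are assumptions.

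**1. Are there two readings?** Both fields exist. The Protocol introduction and SAP Section 2.1 put eligibility first, then agreement, then randomisation; SAP Section 2.3 puts the blood sample one day before the bread. An earlier, separate inclusion value is therefore likely. No passage states it.

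**2. Gain if the two readings are exchangeable.** Let every pair of readings (inclusion, day-before, week 4) have correlation ρ, with equal variance s².
- One covariate: residual variance = (1 − ρ²)s².
- Two covariates: residual variance = [1 − 2ρ²/(1 + ρ)]s².

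| ρ | One covariate | Two covariates | Ratio | Reduction |
|---|---|---|---|---|
| 0.5 | 0.750 | 0.667 | 0.889 | 11% |
| 0.6 | 0.640 | 0.550 | 0.859 | 14% |
| 0.7 | 0.510 | 0.424 | 0.830 | 17% |
| 0.8 | 0.360 | 0.289 | 0.802 | 20% |
| 0.9 | 0.190 | 0.147 | 0.776 | 22% |

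Selecting everyone at 5.0 mmol/L or more on the inclusion value narrows its spread. Simulation with that selection (mean 5.0-6.0, s = 1.0, ρ 0.7-0.9) gives reductions of 9.8% to 20.7%, that is, about 10-21%.

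**3. Gain if the inclusion value is a poorer predictor** (older, or from another laboratory). Let the day-before value correlate 0.75 with week 4, and the inclusion value correlate q with both.
- Day-before value alone: 1 − 0.75² = 0.4375.
- Both: R² = (0.75² + q² − 2 × 0.75 × q²)/(1 − q²).
- q = 0.5: R² = (0.5625 + 0.25 − 0.375)/0.75 = 0.5833; residual 0.4167; reduction 1 − 0.4167/0.4375 = 5%.
- q = 0.6: R² = (0.5625 + 0.36 − 0.54)/0.64 = 0.5977; residual 0.4023; reduction 8%.

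**4. No gain** if the inclusion field repeats the day-before result.

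**5. Cost of the extra covariate in a small trial.** With k covariates and N participants, the expected variance of the adjusted arm difference is inflated by 1 + k/(N − k − 3). The only group sizes given are those of the sequencing subset (14 and 9, SAP Section 2.3.4). At N = 23 the factor is 20/19 for k = 1 and 20/18 for k = 2, so the second covariate costs a factor of 19/18 = 1.056. Reductions of 10% and 21% become 1 − 0.90 × 1.056 = 5% and 1 − 0.79 × 1.056 = 17%. The 8% case becomes about 3%, and the 5% case becomes nil.

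**6. Why the values should not be averaged.** For those selected at 5.0 or more, the inclusion value is expected to exceed a later reading by s(1 − ρ)φ(a)/[1 − Φ(a)], with a = (5.0 − μ)/s. Averaging carries half of this into a before/after change.
- μ = 5.0, ρ = 0.7: 0.3 × 0.798 = 0.239; half is 0.12 mmol/L.
- μ = 6.0, ρ = 0.9: 0.1 × 0.288 = 0.029; half is 0.014 mmol/L.

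This is an apparent fall with no treatment effect. In a within-group paired t-test it raises two-sided type I error from 5% to 5.1-9.6% with 14 in the group, and to 5.3-14.6% with an assumed 26.

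**The case against.** **Two fields are not two blood draws.** This stands. Part A could not apply Table 1 by itself: waist, HDL and blood pressure are on part B, and fasting glucose is time 0 of the OGTT. The cholesterol entry could be an old health-centre result or a copy of the day-before one. The washout sentence covers only pre- and probiotics and does not date the inclusion value. A reader might infer that the trial holds two independent pre-treatment readings and discards one. The documents make that likely but do not show it, so the second covariate is conditional on confirmation.

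**The gain is measured against an analysis that the plan does not contain.** This also stands. The percentages compare two ANCOVAs, and the SAP has neither for cholesterol. They are not a gain over the plan as written, so the missing between-arm model comes first.

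**Not everyone was selected at 5.0 mmol/L.** Correct. Those entering directly on a metabolic syndrome diagnosis need not meet the threshold, so the bias from averaging depends on an unstated mix of entry routes. This does not affect use of the value as a covariate.

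**A single day-before baseline is conventional.** True, and its use is not an error. This point offers an improvement in precision; it does not show that the day-before baseline is biased.

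**Conclusion.** The point holds as a low-cost improvement. For cholesterol, the plan names only paired tests and no between-arm comparison; that is the larger gap. That the paired tests use the day-before value is inferred, because the SAP does not define baseline.

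Given a between-arm ANCOVA, the inclusion value would cut residual variance by about 10-21% if exchangeable with the day-before value, about 5-8% at correlations of 0.5-0.6, and not at all if it is a copy. At the size of the sequencing subset, the spent degree of freedom takes back about 5 percentage points of this. The trial's full size is not given in the text available.

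A reader might extend the argument to body weight, which is also on both forms. The documents do not show that the inclusion weight was separately measured, and no gain has been estimated, so that extension is not supported here.

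**What to change.** 1. State the date, laboratory and source of the inclusion-form total cholesterol, and whether it was drawn before randomisation and separately from the day-before sample.
2. Define baseline as the day-before value.
3. Add a between-arm ANCOVA: week-4 total cholesterol on group, with the day-before value as covariate. Report the adjusted arm difference with its confidence interval.
4. If step 1 confirms a separate pre-randomisation draw, enter the inclusion value as a second covariate with its own coefficient. Do not average it into the change score or into the 10% responder definition.
5. Label the analysis post hoc, because SAP Section 1 says that the document was prepared after the trial was completed.

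The cost is one degree of freedom for the second covariate and a check of source records; no new data are collected. A separate coefficient absorbs a shift or scale difference between laboratories, but not a weaker correlation.
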